4.4.6.2 Impact of Age and Baseline Functional Status on Treatment Effect

Further to the above repeat summaries and analyses by subgroups, an analysis will be conducted to better determine the impact on treatment effect of baseline age and, separately, baseline functional status. This may prompt further post hoc analyses by specific subgroups should this be deemed worthwhile. This analysis will be conducted as described below for each of the following endpoints:

- Change from baseline in 4SC
- Change from baseline in time to rise from the floor
- Change from baseline in 6MWT
- Change from baseline in total NSAA score
- Change from baseline in muscle strength evaluated by knee extension and elbow flexion
- Change from baseline in MRS VL MFF.

Impact of baseline age on treatment effect:

To determine the impact of baseline age, for each of the above endpoints the ANCOVA model described in Section 4.4.2 will be repeated with the addition of the interaction term for treatment by re-derived age at first dose (in years and months). The treatment effect and parameter estimates from the model will be used to plot the treatment effect as a function of age, using:

$$\text{TrtEffect} = B1 + B2 * \text{Age}, \text{ where:}$$

TrtEffect = LS mean difference (givinostat-placebo) for the endpoint

B1 = Parameter estimate for treatment from the model

B2 = Parameter estimate for the treatment by age interaction term from the model

Age = Re-derived age at first dose.

The parameter estimate covariate matrix will be used to compute the variance of the treatment effect as a function of age in order to indicate the confidence interval on the plot.

Impact of baseline functional status on treatment effect:

To determine the impact of baseline functional status for the same endpoints, the ANCOVA model will be repeated again but replacing the treatment by age interaction term with the interaction term for treatment by baseline endpoint value (e.g. treatment by baseline 4SC for the 4SC endpoint). The treatment effect and

parameter estimates from this model will be used to plot the treatment effect as a function of baseline endpoint value, using:

$$\text{TrtEffect} = B1 + B2 * \text{Base}, \text{ where:}$$

TrtEffect = LS mean difference (givinostat-placebo) for the endpoint

B1 = Parameter estimate for treatment from the model

B2 = Parameter estimate for the treatment by baseline endpoint interaction term from the model

Base = Baseline of respective functional endpoint value.

The parameter estimate covariate matrix will be used to compute the variance of the treatment effect as a function of baseline endpoint value in order to indicate the confidence interval on the plot.

4.4.6.3 Presentation of Safety Data by Subgroup

In addition to the above subgroup summaries and analyses of efficacy data, selected summaries of safety data as described in Section 5 will also be repeated by subgroups, for the overall population only.

In order to determine any impact of dose interruptions, modifications or starting dose on safety, the following summaries will be repeated for the subgroups total weight adjusted exposure (mg/kg) < versus >= median total weight adjusted exposure (mg/kg), and higher starting dose (Protocol Versions =< 4.0) versus lower starting dose (Protocol Versions > 4.0):

- All adverse event summaries described in Section 5.1
- All hematology summaries and plots described in Section 5.2.1
- All clinical chemistry summaries and plots described in Section 5.2.2 but restricted to triglycerides only.

4.4.7 Supplementary Analyses

4.4.7.1 Impact of 18 Month Visits Performed Outside of Expected Assessment Windows

As described in Section 2.9, in order to address the impact of the COVID-19 pandemic in terms of 18 month visits performed outside of the expected visit windows, repeated analysis of the primary and key secondary endpoints will be performed using the population of subjects excluding those with visits outside of the window. See Section 2.9 for details.

4.4.7.2 Impact of MRS VL MFF on Functional Treatment Effect Over Time

Further supplemental analyses may be performed if the following criteria are met:

- A significant treatment effect is demonstrated for the imaging key secondary efficacy endpoint (mean change in VL MFF as assessed by MRS before and after 18 months of treatment with givinostat versus placebo),
AND
- Trends over time are observed for the primary endpoint either with or without a significant treatment effect.

In the case that these criteria are met, the data will be reviewed to determine whether to proceed with further supplementary analyses exploring the extent to which treatment effect on the primary endpoint is influenced by the treatment effect on MRS VL MFF over time, thus suggesting a potential functional benefit over a longer follow-up period. Where this analysis is deemed beneficial, the supplementary analysis of the primary endpoint will be conducted as described below.

A mixed effects model with repeated measures (MMRM) will be fitted to the change from baseline in the primary endpoint to each post-baseline visit at which the endpoint is assessed. The model will include baseline values for: 4SC, time to rise from floor, time to run/walk 10 metres, distance walked in 6 minutes and re-derived age at first dose (in years and months) as covariates, concomitant steroid use (according to the 4 possible strata), treatment and visit as fixed effects and the treatment by visit interaction. F-tests from PROC MIXED will be based on Kenward-Roger's adjusted degrees of freedom. An unstructured variance/covariance matrix will be used for the repeated visits within a subject.

The above model will then be repeated with the addition of the following terms: MRS VL MFF value at each visit, MRS VL MFF by visit interaction, MRS VL MFF by treatment interaction, MRS VL MFF by treatment by visit interaction.

For each of the two models, the following will be presented and used to assess whether the treatment effect is reduced by the addition of MRS VL MFF to the model: for each visit included in the model, adjusted least squares means and associated 2-sided CIs will be estimated and presented for givinostat and placebo. The treatment effect at each visit, being the difference in adjusted least squares means (givinostat-placebo), will also be presented along with the associated 2-sided CIs and p-values.

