12. During the screening period (i.e., 4 weeks  $\pm$ 2), time to 4-stair climb test (4SC) should be performed at V1 and V2. The 4SC at V2 can be performed one day after V1 up to a maximum of 2 weeks (+3 days). For this reason the subjects should go to the centre 2 times (i.e., Visit 1 and Visit 2). The test should be video recorded during Visit 1, Visit 3, Visit 13 and Visit 15.
13. Muscle strength tests: at screening: knee extension, elbow flexion by HHM and knee extension by MMT. During the study and at the end: knee extension, elbow flexion by HHM.
14. Pharmacokinetic sample collection: sampling (2 pre-dose during the treatment and 4 post-dose) will be collected as described in the protocol during the following visits: 7 (4 weeks), 10 (12 weeks), 11 (24 weeks), 13 (Week 48) and 15 (Week 72). At these visits, the subject will be asked to take the morning dose at site.
15. The baseline MRI/MRS test has to be performed when all inclusion/exclusion criteria have been already evaluated and the subject is eligible. At screening all subjects will perform the MRI of thigh and MRS of vastus lateralis; then the MRI of thigh and MRS of vastus lateralis will be performed also at 12 and 18 months in a subgroup of subjects: the first 99 - 150 randomised subjects in the target population (i.e. with MRS VL MFF between  $>$  5% and  $\leq$ 30%). The MRI evaluation using Dixon technique and the MRS will be performed at specialized sites.
16. Genetic test should be performed only in case it is not already available.

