#### **9.1.7 Visits 10 – 14 (Weeks 12-60, $\pm$ 7 days)**

The Visits 10, 11, 12, 13 and 14 will respectively happen after 12, 24, 36, 48 and 60 weeks after the Randomization Visit, with a visit window of  $\pm$  7 days.

At Visit 10 – 14 (i.e., every 3 months), the following assessments will be performed unless otherwise noted:

- Collect and record concomitant medications;
- Perform a physical examination;
- Measure vital signs (blood pressure, pulse rate, and body temperature);
- Measure weight;
- Measure height (only at Visits 11 and 13; i.e., after 6 and 12 months of treatment) ;
- Perform a 12-lead ECG (at 2,5 hours  $\pm$ 30 minutes after drug intake);
- Perform pulmonary function tests: FEV1, FVC, FEV1/FVC, and PEF (only at Visit 13);

Pulmonary function as assessed by spirometry at visit 13 should be repeated if the test does not meet ATS/ERS criteria and/or the evaluator deems that a valid attempt to perform a correct maneuver has not been made by the subject.

- Collect blood samples for:
  - hematology;
  - blood chemistry;
  - coagulation tests (PT and aPTT);
- Collect DMD serum biomarkers (only at Visit 13);
- Obtain a urine sample for urine analysis;
- Perform Quality of Life tests (assessed by PODCI) (only at Visit 13; i.e., after 12 months of treatment);
- Perform time to 4SC
- Perform NSAA and 6MWT;
- Perform muscle strength tests;
- Obtain PK blood sample (only at Visits 10, 11, and 13; i.e., after 3, 6, and 12 months of treatment, respectively);

- Dispense and account for study drug;
- Subject diary dispensation and evaluation of drug compliance through diary;
- Assess AEs;
- Perform MRI/MRS evaluation (MR cohort only) (only at Visit 13; i.e., after 12 months of treatment).

At Visit 13, functional tests will be video recorded.

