**9.1.8 Visit 15: End of Study Visit (also named “EOS Visit”, Week 72 ± 7 days), and early withdrawal visit**

At the end of the treatment (i.e., 72 weeks after the Randomization Visit, ± 7 days) the EOS Visit (Visit 15) will be scheduled. At EOS Visit the subject should take the morning dose at the site.

Subjects who prematurely withdraw from the study for any reason will perform an Early Withdrawal Visit within two weeks after the last study drug dose intake. The Early Withdrawal Visit requirements are the same as the EOS Visit (Visit 15) described in this section.

If the Early Withdrawal Visit or the EOS Visit is not done, the reason will be recorded in the CRF.

At this Visit 15, the following assessments will be performed unless otherwise noted:

- Collect and record concomitant medications;
- Perform a physical examination (at V15 assessment for ankle ROM should be done)
- Measure vital signs (blood pressure, pulse rate, and body temperature);
- Measure weight;
- Measure height;
- Perform a 12-lead ECG (at 2,5 hours ±30 minutes after drug intake);
- Perform an ECHO;
- Perform pulmonary function tests: FEV1, FVC, FEV1/FVC, and PEF;
- Collect blood samples for:
  - hematology;
  - blood chemistry;
  - coagulation tests (PT and aPTT);
- Collect DMD serum biomarkers;
- Obtain a urine sample for urine analysis;

- Obtain PK blood sample. The remaining PK samples may be drawn during this visit in order to obtain all required PK samples;
- Perform Quality of Life test (assessed by PODCI);
- Perform time to 4SC
- Perform NSAA and 6MWT;
- Perform muscle strength tests
- Perform cognitive function evaluation (test should be performed at the beginning and at the end of the study, at the same time of the day);
- Perform acceptability/palatability evaluation;
- Evaluation of drug compliance through diary;
- Assess AEs;
- Perform MRI/MRS evaluation (MR cohort only). (If the subject is discontinued from the study treatment, the subject will be asked to return for the early withdrawal visit to be performed within 2 weeks of the last dose of study drug. In this case, the cognitive function evaluation and MRI/MRS may not be performed).

Functional tests will be video recorded.

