2.3 Study Design

This is a Phase 3, randomised, double blind, placebo controlled, multicentre study to evaluate the efficacy and safety of givinostat in ambulant subjects with DMD. This

study will include ambulant male paediatric subjects aged ≥ 6 years at baseline affected by DMD.

A target population (Group A) will consist of subjects with a baseline vastus lateralis muscle fat fraction (VL MFF) assessed by Magnetic Resonance Spectroscopy (MRS) in the range $> 5\%$ and $\leq 30\%$. An off-target population (Group B) will consist of subjects with a baseline VL MFF assessed by MRS in the range $\leq 5\%$ or $> 30\%$. The target and off-target population assignments will be derived from the actual VL MFF values entered onto the electronic Case Report Form (eCRF) at baseline. If for any reason this information is missing or it is not possible to determine the assignment from the VL MFF results recorded, the subject will be classified as off-target. Following collection of MRS VL MFF data, a blinded central review of the data will be conducted by University of Florida Imaging DMD network, which may lead to adjustment of some VL MFF results. The final VL MFF results following blinded review (external to the eCRF) will be used for analyses of MRS data (see Section 4.2.2). However, the assignment to target and off-target populations based on the initial values entered onto the eCRF will not be adjusted for any changes in baseline MRS VL MFF results from blinded review.

All subjects in the target population will undergo the magnetic resonance assessment at baseline, 12 and 18 months and will be eligible for inclusion in the Magnetic Resonance (MR) Cohort defined in Section 3.1.1.

A total of 110 male ambulant subjects in the target population are planned to be randomised (Group A). In addition, it is planned that up to 50 subjects (about 35% of the overall population) outside of the target population may also be recruited into the study (Group B). The overall subject population (Group A + Group B) will provide supportive data.

At the randomisation visit, in addition to the continued standard of care corticosteroids regimen, DMD subjects will be randomised in a 2:1 ratio to receive givinostat oral suspension 10mg/mL or placebo oral suspension b.i.d. in a fed state.

At randomisation, subjects will be stratified for their concomitant use of steroids in 4 strata:

1. Deflazacort daily regimen
2. Deflazacort intermittent regimen
3. Other steroids daily regimen

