4.3.7 Time to Persistent Loss of Standing (Baseline Through End of Study)

Functional assessments are scheduled to take place every 3 months. In order to allow time for recovery due to trauma, a subject will be considered to have persistent loss of standing if they are unable to stand for at least 2 consecutive assessments (i.e. at least 6 months). Start of a persistent loss of standing will be the first assessment where this is observed. A subject is unable to stand if their score for "Rise from floor" on the NSAA assessment is 0b ("Unable") and if their rising from floor grading is 1 on the Rise from floor assessment. If a subject has not met the criteria for persistent loss of standing by the end of the study, the time to persistent loss of standing will be censored at the date of the last NSAA or Rise from floor assessment (including imputed assessments per Section 4.4.4.1), i.e. the 18 month assessment.

The number and percentage of subjects who have persistent loss of standing at any point post-baseline, as well as those censored, will be summarised by treatment group. Time to persistent loss of standing will be calculated as the time from the date of first study treatment to the start of the first occurrence of persistent loss of standing. The Kaplan-Meier estimates of the median, 25th percentile and 75th percentile for time to persistent loss of standing, together with the associated 2-sided 95% CIs will also be presented by treatment group. Time to persistent loss of standing will also be presented graphically by treatment group using a Kaplan-Meier plot.

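### The supplementary 4SC model adds VL MFF at every visit, but MRS exists at only two of the six visits, so the two models being compared do not rest on the same rows

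*SAP*

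**What the plan says.** SAP 4.4.7.2 describes an analysis that may be run if VL MFF shows a significant treatment effect and 4SC shows trends over time, and if a review of the data then finds it worthwhile. The first model is an MMRM for the "change from baseline in the primary endpoint to each post-baseline visit at which the endpoint is assessed". It has baseline functional covariates, age, steroid stratum, treatment, visit and treatment by visit, with an unstructured covariance. The second is the same model plus "MRS VL MFF value at each visit, MRS VL MFF by visit interaction", and VL MFF interactions with treatment and with treatment by visit. Each model reports a treatment effect at every visit it contains. The pair is used to judge whether the effect falls once VL MFF is included, and a fall is taken to hint at functional benefit over longer follow-up.

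On when 4SC is measured, Protocol 9.1.7 says "The Visits 10, 11, 12, 13 and 14 will respectively happen after 12, 24, 36, 48 and 60 weeks" and lists 4SC at these visits. Protocol 9.1.8 adds "Perform time to 4SC" at week 72. SAP 4.3.7 agrees: "Functional assessments are scheduled to take place every 3 months".

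On when MRS is done, SAP 2.3 says "All subjects in the target population will undergo the magnetic resonance assessment at baseline, 12 and 18 months". Protocol Table 6, footnote 15, says after the screening scan that "MRS of vastus lateralis will be performed also at 12 and 18 months". Among Visits 10 to 14, Protocol 9.1.7 has "Perform MRI/MRS evaluation (MR cohort only) (only at Visit 13; i.e., after 12 months of treatment".

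**The concern.** Asking whether an effect shrinks when a covariate is added is informative only if nothing else changes between the two fits. Here the covariate does not exist at four of the six visits in the first model. The second model therefore either cannot be fitted at those visits or silently becomes a two-visit model, and the text does not say which. The difference between the two treatment effects then mixes two things: the addition of VL MFF, and a change in the data used. What is at stake is the reading of one supportive analysis, namely how far the 4SC effect moves with the VL MFF effect.

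**Working it through.** **1. Visits.** From Protocol Table 6, 9.1.7 and 9.1.8, and SAP 2.3:

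| Month | 3 | 6 | 9 | 12 | 15 | 18 |
|---|---|---|---|---|---|---|
| 4SC | yes | yes | yes | yes | yes | yes |
| MRS of vastus lateralis | no | no | no | yes | no | yes |

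4SC has 6 post-baseline visits and MRS has 2.

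**2. Rows.** With the planned 110 target subjects, the first model has 110 × 6 = 660 scheduled rows. The second has at most 110 × 2 = 220. The share without VL MFF is 1 − 220/660 = 67%. This assumes that a row with a missing covariate is left out of the fit, which the SAP does not state.

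**3. Does another rule fill the gap?** SAP 4.4.4.1 imputes missing values at scheduled timepoints, and MRS is not scheduled at months 3, 6, 9 or 15. Class 1 imputation also uses the mean of non-missing values at the same timepoint, and at those four visits there are none. Section 4.4.7.2 gives no carry-forward, interpolation or joint-modelling rule. None of the four changes in SAP Addendum 1 concerns this section.

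**4. Analysis set.** SAP section 4 puts efficacy analyses on the ITT set, except those presenting MRI/MRS data, which use the MR cohort. Section 4.4.7.2 does not say which set applies to either model. By SAP 3.1.1, a treated target boy with a post-baseline 4SC but no post-baseline scan is in ITT and outside the MR cohort. The documents do not say how many such boys there are.

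**5. Where the treatment effect is evaluated.** With the added interactions, the second model's effect at visit v and VL MFF value m is τ(v) + [γ + γ(v)] × m. It depends on m, and the SAP does not give m.

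**6. What changing the rows alone does.** The first model's covariates have no interaction with visit. With complete data, its estimate at visit v is therefore: (difference in mean 4SC change at v) − (baseline covariate imbalance) × (common covariate coefficients). The first part is the same whichever other visits are in the fit. Only the coefficients change.

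To gauge the size, 500 trials were simulated and the model without VL MFF was fitted to all six visits and then to months 12 and 18 only. These inputs are assumptions, not document figures:

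- 110 subjects randomised 2:1, with complete data.
- A true effect of 2 s at month 18, growing linearly.
- A residual SD of 3 s at month 18.
- A correlation of 0.85 between adjacent visits, decaying with distance.
- Five baseline covariates whose influence grows with time; steroid strata omitted.

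Results at month 18:

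- Mean effect −1.986 s on six visits and −1.982 s on two, so a mean shift of −0.004 s.
- SD of the shift 0.143 s; central 95% range −0.30 to +0.28 s.
- A shift larger than 0.2 s (0.2/2 = 10% of the effect) in 14% of trials.
- Average standard error of the month-18 effect 0.640 s (six visits) and 0.616 s (two visits), so the shift's SD is about 0.143/0.640 = 22% of a standard error.

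The month-12 shift has the same mean and SD, as the formula predicts.

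**The case against.** The strongest reply is that both models report effects visit by visit. A sensible reader would compare month 12 with month 12 and month 18 with month 18, and ignore the visits without a counterpart. In the simulation, the change of rows moved those contrasts by about zero on average. The analysis is also optional, triggered only under stated conditions, carries nominal p-values, and is worded as exploration. All of this stands, and it limits the weight of the point. It does not remove it: the text still asks for a model that cannot be fitted as described, and even the like-for-like contrasts carry avoidable noise.

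A reader might infer that boys with a missed scan fall out of the second model. The documents do not support that. SAP 7.5.6 makes every missing VL MFF value Class 1, SAP 4.4.4.1 imputes it at months 12 and 18 (including after withdrawal), and SAP 2.8 carries imputed values into all analyses. A difference in subjects arises only if the first model is run on ITT and the second on the MR cohort.

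A reader might also take the 67% as a measure of distortion. It counts rows and says nothing about how far the month-12 or month-18 effect moves.

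**Conclusion.** The point holds as a specification fault of low weight. As written, the second model cannot estimate effects at months 3, 6, 9 and 15. A change in the month-12 or month-18 effect between the models reflects partly the different rows, and possibly a different analysis set, and not VL MFF alone.

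On the assumed inputs the row change adds noise with an SD of about 0.14 s to a 2 s effect, with no systematic direction. The stronger inference, that data selection alone could produce the appearance of benefit working through VL MFF, is not supported. The size rests on complete data, on the assumed correlation and covariate pattern, and on rows without VL MFF being dropped. The visit count rests on the documents alone. No primary or key secondary result depends on this analysis.

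**What to change.** Amend SAP 4.4.7.2 for this comparison:

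- Fit both models to one named analysis set, the MR cohort, and to the same subject-visits, months 12 and 18.
- Keep the SAP's Class 1 imputation for missed scans. Restricting to boys with an observed scan would depart from the SAP's own rule and would select on a post-randomisation event.
- State the VL MFF value at which the second model's least squares means are evaluated. The first model has no VL MFF term, so this applies to the second only.
- Describe the result as associational.

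The cost is a paragraph of SAP wording and no new data. The first model loses the early visits and month 15, for this comparison only. The six-visit model can still be reported separately. Constructing VL MFF at the other visits would keep all six, but four of every six values would then be assumed and not measured.
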